The Co-TELE-SURGE Study

Preoperative and postoperative Cognitive TrajEctories in oLdEr patients with
deferred SURGEry due to the COVID-19 emergency:
a prospective cohort study

Short title (max 25 characters): Deferred surgery @COVID19

Protocol Version 3
May 31, 2020

STUDY SUMMARY

Title	The Co-TELE-SURGE Study Preoperative and postoperative Cognitive Trajectories in o ld er patients with deferred SURGE ry due to the COVID-19 emergency: a prospective cohort study
Project Office	Department of Health Research Methods, Evidence, and Impact McMaster University [name]
Study Size	330 patients
Study Design	Multicentre, prospective and longitudinal, cohort study
Primary Objectives	In older patients whose elective noncardiac surgery has been deferred because of the COVID-19 emergency, 1) to describe perioperative cognitive trajectories, and 2) to explore the intra-individual changes in these trajectories from before to after surgery.
Secondary Objectives	In older patients whose elective noncardiac surgery has been deferred because of the COVID-19 emergency, 1) to describe the perioperative trajectories in depressive symptoms and pain, and 2) to explore their association with the trajectories in cognitive performance.
Eligibility Criteria	
Inclusion criteria
 
 1. age 65 years or greater 2. patient scheduled to perform noncardiac elective surgery expected to require at least an overnight stay in hospital after surgery 3. surgery deferred, with a known or probable surgery date in ≥ 6 weeks 4. informed consent provided 
Exclusion criteria
 
 1. patient undergoing cardiac surgery, or cranial surgery 2. known history of dementia 3. unavailability of tablet or computer with an internet connection for remote assessment 4. patient unable to interact with a tablet or computer due to language, visual, or hearing impairment, or any severely limited mobility of the upper limb joints 5. patient unable to understand spoken or written English 6. surgery delayed for a intercurrent clinical event
Follow-up and measurements	At enrolment and monthly before surgery (i.e. ≥ 2 preoperative assessments per patient), and then 1 month, 3 months, 6 months, and 12 months after surgery, patients will be assessed remotely 
 1. on their cognitive performance, through a computerized brief cognitive test battery, self-administered, i.e. the Cogstate Brief Battery (CBB) 2. on their physical function/mobility, through the Function Component of the Late-Life Function and Disability Instrument (LLFDI-FC) and exploring life space mobility

	
3. on their depressive symptoms, through the short form (15-item) version of the Geriatric Depressive Scale (GDS)4. on their pain, through a Numeric Pain Rating Scale (NPRS)
--	--

Table of Contents

1. BACKGROUND AND RATIONALE.....	5
2. OBJECTIVES.....	6
3. METHODS	6
3.1 Study design.....	6
3.2 Study population.....	6
3.2.1 Inclusion criteria.....	7
3.2.2 Exclusion criteria.....	7
3.3 Recruitment and procedures	7
3.4 Measurements	8
3.4.1 Cogstate Brief Battery (CBB).....	8
3.4.2 Changes in activities and participation since COVID-19 questionnaire.....	9
3.4.3 Late Life Function and Disability Instrument: Function Component (LLFDI-FC).....	9
3.4.4 Geriatric Depression Scale (GDS).....	10
3.4.5 Numeric Pain Rating Scale (NPRS)	10
3.5 Sample size.....	10
3.6 Data analysis plan.....	11
3.6.1 Primary analysis.....	11
3.6.2 Secondary Analyses	12
4. IMPORTANCE OF THE STUDY	12
APPENDIX I. Study timeline, measurements, and data collection	14
APPENDIX II. Performance at the Cogstate One-Back Task (OBK): interpretation and clinical relevance of changes in score.....	15
APPENDIX III. Changes in activities and participation since COVID-19 questionnaire	16
REFERENCES.....	17

1. BACKGROUND AND RATIONALE

The COVID-19 emergency has been impacting our patients and healthcare systems in several ways. To redeploy resources (staff and equipment) to priority areas, ensure hospital capacity to front the COVID-19 surge, and for infection control reasons, the use of operating rooms have been limited mainly to semi-urgent (e.g., oncology), urgent (e.g., hip fracture) and emergency (e.g., ruptured abdominal aortic aneurysm) surgeries, while many elective surgeries have been deferred to a later, often undermined, time. From a societal perspective, this is certainly thought to be the best choice in such an emergency. From an individual perspective this is going to represent a stressful situation for those patients, often older, whose surgery is not happening as planned.

On the other side, from an epidemiological perspective, this represents a unique opportunity to study the impact of surgery on cognitive performance. Postoperative cognitive dysfunction (POCD) is an objectively measured decline in cognition postoperatively compared with preoperative function.^{1,2} The NeuroVISION study demonstrated that as many as 30% of patients aged 65 or older undergoing elective noncardiac surgery experience cognitive decline at 1 year after surgery, defined as ≥ 2 point decline in the Montreal Cognitive Assessment compared with before surgery.³ This has questioned the role of surgery in cognitive decline. Many of these patients have several comorbidities, which, in addition to age, could theoretically impact their cognitive performance over time. Therefore, it is still uncertain whether the decline we see in these patients who underwent surgery is different from what we would have seen if the same patients had not undergone surgery. An epidemiological study could try to answer this question comparing the surgical cohort with a matched non-surgical cohort. However, whatever matching approach we use, the control group is always going to be imperfect, and undoubtedly inferior to an approach that compares the individual with themselves. However, when we evaluate the effect of surgery comparing the patient cognitive performance at a certain time point after surgery with the cognitive performance measured at only one time point before surgery, we miss considering a possible pre-existing trend over time before surgery, which could hypothetically explain the change after surgery.

While for some surgeries, a waiting time to surgery of months is not an unusual eventuality (e.g., some elective orthopaedic surgeries), this is a more unique circumstance for other major elective noncardiac surgeries. Therefore, to identify surgical candidates time before their surgery, and follow them up for a certain time before their surgery is often impracticable. Due to the COVID-19 contingency, we now have a sample of patients that, due to the deferral of their surgery we are capable of following and assessing for their cognitive status before they receive their surgery, for one to a few months. In this way, we will be able to draw preoperative individual-specific trajectories of cognitive performance, which represent an intra-individual comparison to the postoperative cognitive performance, to evaluate the relative and absolute impact of surgery on our older patients.

We expect that the COVID-19 pandemic, and the imposed social distancing, is having an impact on older patient lives, and also on older patients that are waiting for their surgery. Changes in their ability to live a normal life because of the current restrictions might translate into changes in their physical performance, and might have an impact on their mood and also on their perception of pain, and eventually translate into changes in their cognitive performance. The deferral of their surgery *per se*, and the possible adoption of adjuvant

therapies in the meantime, might have, at least theoretically, an influence on their overall performance. For all these reasons, we might see a different preoperative cognitive trajectory, compared with what we would have seen in a non-COVID-19 time. However, if surgery has an impact on our patient cognition, we still expect to see it as a postoperative change (e.g. a greater decline, a change in slope) compare to their actual preoperative trajectory, so that the performance we see at 3, 6 or 12 months after surgery is worse than what we would expect based on the preoperative trajectory.

The use of computerized cognitive testing in older people has incredibly expanded in recent times. The existing literature confirms the strengths of this approach, which include standardization of administration and stimulus presentation, accurate measures of response, and efficiencies of staffing and cost, and supports feasibility and acceptability.^{4,5} Computerized testing allows also for remote cognitive assessment, which has been shown feasible and reliable also in older subjects, also with some cognitive impairment.^{6,7} In the era of physical and social distancing imposed by the COVID-19 emergency, this is particularly relevant. Moreover, since virtual and telecommunication tools have become a daily vehicle for maintaining some type of encounter with our patients, more older patients are becoming familiar with these types of encounters and tools.

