3.4.3 Late Life Function and Disability Instrument: Function Component (LLFDI-FC)

The Function Component of the Late-Life Function and Disability Instrument (LLFDI-FC) is a widely used patient-reported outcome of physical function.^{14 15} It comprehensively assesses discrete functional tasks and operationalizes disability in important life roles beyond the narrow construct of activities of daily living. Extensive evidence supports its construct validity and sensitivity to change among various clinical populations of community-dwelling older adults.¹⁶ The instrument will be administered over the phone by the research personnel at each follow-up, preoperatively and postoperatively. Three additional questions will be also asked to explore life space mobility (being just outside the house, being in the neighborhood, and being outside

the neighborhood), which will also capture changes in social distancing policy that we expect will happen over the study period. At the end of the mobility questionnaire, the participants will be also asked whether there have been changes in their ability of performing basic and instrumental activities of daily living.

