3.5 Sample size

The slowdown of the operating rooms due to COVID-19 started in mid-March, and it will last at least until the end of June or July at the participating sites. We expect to recruit 330 participants between May and August 2020. This sample size will be sufficient to test our primary hypothesis that, on average, in our population, the cognitive performance at 6 months after surgery will be worse, in a clinically significant way, compared to what we would expect based on the preoperative trajectory. We will base our primary hypothesis on the performance at the *One-Back Task (OBK)* of the CBB, at 6 months after surgery. The *OBK* assesses working memory, which is a cognitive domain often found altered in the context of postoperative cognitive dysfunction. It uses a well-validated n-back paradigm with stimuli from playing cards. The subject is asked whether the card displayed in the center of the screen is the same as the card presented immediately before. The subject responds by pressing the “yes” or “no” key. The primary outcome variable for this test is accuracy of correct response, normalized using an arcsine square-root transformation. In **APPENDIX II** we provide a table summarizing the clinical relevance of the test and its results, with data on the difference in performance between healthy older adults, and older adults with mild cognitive impairment (MCI) or dementia based on standardized neuropsychological assessment.^{13 19} Based on the literature, a typical score of healthy older adults is 1.35; the average difference, at one time point, in the *OBK* score, between healthy older adults and older adults with mild cognitive impairment (MCI), and older adults with dementia, is, respectively, 0.07 and 0.17.^{13 19} We hypothesize that in our study population we will see a preoperative trajectory, which, if it continued, unchanged, after surgery (H_0), would lead to an average decrease in OBK score of 0.009 over 6 months. This is still consistent with a decline over time compared with what we would expect on average in a healthy older population.^{13 19} Our hypothesis (H_1) is that surgery will change the preoperative trajectory so that at 6 months after surgery we will instead see an average decrease, compared with right before surgery, of 0.035 (which would correspond to the average change in a hypothetical population in which 40% of subjects experience a decline of at least 0.07, 50% no

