change, and 10% an improvement of 0.07). Based on a test of comparison of means in one sample, with an alpha error of 0.05 (2-tailed), and a standard deviation for the OBK score of 0.16,¹³ to enrol 330 subjects will be sufficient to test our hypothesis with 80% of power, even in case of an attrition rate as high as 10%.

Recruiting 330 participants is a feasible goal based on the current status of knowledge about the COVID-19 contingency plan. The lockdown of the operating rooms started in March and will last at least until the end of June, or longer, depending on the participating site. During the lockdown, we expect to be able to enroll at least 120 participants at McMaster sites, and 30-50 participants at each of the other participating sites. Even when the operating rooms will reopen to more elective surgeries in the next months, this will happen slowly, so that we expect a carryover of the lockdown at least until the end of the summer. Moreover, it is projected that, if countries increase their normal surgical volume by 20% post-pandemic, it would take a median 45 weeks to clear the backlog of operations resulting from COVID-19 disruption.²⁰ Therefore should we see a recruitment rate slower than expected, for any reason, we will extend our recruitment period to beyond the summer.

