3.6.1 Primary analysis

We will report descriptive summary statistics of the performance of the study population at each of the 4 CBB tasks for each of the preoperative and postoperative time points. We will also represent individual and averaged performance trajectories graphically.

To explore whether surgery has a statistically significant impact on cognitive performance and its trajectories, we will model data using interrupted time series analyses. Interrupted time series analysis is a powerful quasi-experimental design to study the longitudinal effects of interventions or exposures, accounting for pre-intervention/pre-exposure trends. We will adopt the approach described in Kontopantelis *et al.*, *BMJ* 2015.^{21 22} According to this approach we will use regression models in which the within patient performance variation over time is partitioned into three main components, to provide independent tests for the slope in scores in the pre-operative period (test 1); the change in level (i.e., absolute change) around surgery, allowing for the trend before surgery (test 2); and the change in slope from before to after surgery (test 3).^{21 22} The preoperative slope quantifies the trend in performance before surgery. The level change is an estimate of the absolute change in cognitive performance that can be attributed to surgery, i.e., between the time points immediately before and immediately after surgery, and accounting for the preoperative trend. The change in slope quantifies the difference between the preoperative and postoperative slope. Based on the hypothesis that the postoperative trajectory will not be homogenous over the 12 months after surgery, we will also adopt a more complex interrupted time series model that will allow for different slopes of change in different time segments, i.e. right before to 1 month after surgery, 1-3 months, 3-6 months, and 6-12 months after surgery.²³ We will conduct the primary analysis first considering only the early-intermediate postoperative performance (up to 6 months after surgery). With the assumption that the

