3.6.2 Secondary Analyses

We will explore whether the effect of surgery on cognitive trajectories differ based on baseline patient characteristics, including age, type of surgery, cognitive performance at baseline, comorbidities, mobility, GDS and pain score. This will be done studying the interaction of these covariates with the components of the interrupted time analysis. The interrupted time series approach as described assumes linearity and constancy of the preoperative trend when projected postoperatively. We will evaluate the validity of these assumptions exploring the association of changes in cognitive performance with intercurrent events other than the index surgery, for the long-term effects.

With a similar approach as for the cognitive performance, we will study the perioperative trajectories of patient physical function/mobility (as indicated by the LLFDI-FC and the life space mobility questions), depressive symptoms (as indicated by the GDS), and of pain (as indicated by the NPRS). We will also explore whether the time-dependent LLFDI-FC, GDS and NPRS scores are associated with the time-dependent cognitive scores.

STATA software, version 15, will be used for the analyses.

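### The primary interrupted time series has no calendar term, so a non-linear pandemic effect can bias the 6-month surgery contrast in either direction

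*Combined protocol and SAP*

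**What the plan says.** - **Restrictions may affect cognition.** Section 1 traces a path from distancing and surgery deferral through function, mood and pain to cognitive performance. It answers the difficulty by saying that, if surgery has an effect, "we still expect to see it as a postoperative change" relative to the actual preoperative course.
- **Policy will move.** Section 3.4.3 adds three life-space questions at each follow-up, "which will also capture changes in social distancing policy that we expect will happen over the study period".
- **The model.** Section 3.6.1 splits within-patient change into a preoperative slope, a level change and a slope change, with a second version that allows separate postoperative segments. No calendar, policy or site-period term is listed. On interpretation it says: "The level change is an estimate of the absolute change in cognitive performance that can be attributed to surgery".
- **The assumption check.** Section 3.6.2 acknowledges that the method assumes a linear, constant preoperative trend. It checks this against intercurrent events, which section 3.4 and Appendix I define as admissions, emergency or urgent-care visits and medication changes.
- **Related secondary work.** Section 3.6.2 treats life-space as a trajectory outcome and will explore "whether the time-dependent LLFDI-FC, GDS and NPRS scores are associated with the time-dependent cognitive scores".

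**The concern.** In an interrupted time series without a concurrent control series, the main threat is another exposure that changes near the interruption. The protocol names such an exposure, expects it to change, and collects data that track it. Even so, it enters neither the main contrast nor the check of the main assumption.

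The section 1 argument works if the pandemic effect is constant or linear over calendar time, because the preoperative slope then absorbs it. It does not work for a step, a ramp or a reversal. Surgery dates depend on operating rooms reopening, which may well move together with wider restrictions. At stake is whether a departure from the projected trajectory at 6 months can be read as an effect of surgery, when the planned difference is small.

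**Working it through.** **1. The plan's own figure.** Section 3.5 states: "would lead to an average decrease in OBK score of 0.009 over 6 months" under the null, and under the alternative an "average decrease, compared with right before surgery, of 0.035". The difference is 0.035 - 0.009 = 0.026. The test is a one-sample comparison of means "with an alpha error of 0.05 (2-tailed), and a standard deviation for the OBK score of 0.16", with 80% power and 10% attrition.

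n = [0.16 × (1.960 + 0.842) / 0.026]² = 297.2, and 297.2 / 0.9 = 330.3. The planned 330 reproduces. The planning standard error is 0.16 / √297 = 0.0093. The present point does not alter this calculation.

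**2. Mechanism.** Take single patients with no surgery effect, tests at months -2, -1 and 0, and a lasting reopening effect b.
- *Reopening before the first test:* every score is shifted by b, so the contrast is 0.
- *Reopening between the last two preoperative tests:* scores are 0, 0, b. The slope is b/2 per month and the fitted value at month 0 is b/3 + b/2 = 5b/6. The projection to month 6 is 5b/6 + 6 × b/2 = 23b/6. The observed value is b, so the contrast is b - 23b/6 = -2.83b: a false decline if b is positive.
- *Reopening after the last preoperative test:* the projection is 0 and the observed value is b. The contrast is +b, which would hide a decline.

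The pooled result mixes these cases, so both sign and size depend on timing.

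**3. Pooled contrast.** A patient fixed-effects segmented regression was fitted to data up to 6 months, with no true surgery effect. From the protocol: enrolment May to August 2020 (section 3.5), a wait of at least 6 weeks (3.2.1), monthly preoperative tests, and tests at 1, 3 and 6 months (3.4.1). Assumed: uniform enrolment, the longest wait, and the date and shape of reopening. A selection of the 18 schedules:

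| Longest wait | Reopening | Shape | False 6-month contrast |
|---|---|---|---|
| 90 days | 1 August | step | -1.10b |
| 90 days | 1 September | step | -0.85b |
| 90 days | 1 September | 90-day ramp | +0.38b |
| 180 days | 1 August | step | -0.90b |
| 300 days | mid-June | step | -0.21b |
| 300 days | 1 September | step | -0.66b |

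Seventeen of the 18 were negative. Across these schedules 7% to 97% of preoperative tests fell before reopening. Further sets of reopening dates and waits gave -1.25b to +0.67b and -1.15b to +0.70b, so the overall range is roughly -1.25b to +0.7b.

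**4. Scale.**
- b = 0.01: -0.0125 to +0.007, or 48% and 27% of 0.026.
- b = 0.02: -0.025 to +0.014, or 96% and 54% of 0.026.

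At the planning standard error of 0.0093, a bias of 0.013 with no surgery effect raises the rejection rate to 29%. If it masks a true 0.026, power falls to 29%. The segmented model is less precise than the planning formula. In a simulation with assumed reliability 0.7 its standard error was about 0.018, and a bias of 0.012 then gives about 10% rejection.

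**5. Does a calendar term help?** A single reopening indicator removes the bias when reopening really is a step. With a 3-month ramp, up to 0.73b remained; with a temporary easing, the indicator sometimes increased the bias. Calendar-month effects removed nearly all of the bias in every schedule checked. The standard error rose by about 0-17% with the indicator and 12-20% with month effects.

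The linear component has to be left out. Within a patient, calendar time and time from surgery differ only by a constant, so a linear calendar term duplicates the preoperative slope. It also does no harm, because that slope carries it through.

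**The case against.** The strongest reply has four parts.

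- **No size is known.** The documents contain no estimate of a reopening effect on the One-Back score, and b might be negligible. For context, 0.02 is 29% of the 0.07 difference between healthy adults and those with mild cognitive impairment in Appendix II (0.02/0.07). This stands: every bias figure here is conditional.
- **The timing is not a clean split.** A reader might infer that preoperative tests fall in lockdown and postoperative tests in reopening, so that the direction of bias is known. The documents do not support that. The lockdown in section 3.5 is of operating rooms, no date for easing of distancing is given, recruitment may run past the summer, and waits have no upper limit. This stands, and it is why no sign is claimed.
- **The protocol is partly aware.** Section 2 sets out to describe and explore, and 3.6.2 states the constancy assumption. But section 3.5 sets a primary hypothesis at 6 months, and 3.6.1 uses causal wording for the level change. It does not use that wording for the slope change, and the point should not be stretched to say so.
- **Life-space is not ignored.** A reader might infer that it was dropped from the association analysis. Section 2 commits to relating mobility and function to cognition, and 3.6.2 counts life-space within mobility. Its absence from the list of time-dependent scores is at most a wording gap.

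A calendar term also has limits. It treats patients still waiting as subject to the same calendar effects as those already operated on. The order of surgery need not be random, and few patients may still be waiting when others reach 6 months.

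**Conclusion.** The concern holds as a gap in the analysis plan. The protocol anticipates a changing influence on cognition, but neither models it in the primary analysis nor includes it in the assumption check. The 6-month surgery contrast is therefore open to bias of unknown sign from any non-linear calendar effect. For an assumed reopening effect b the bias is roughly -1.25b to +0.7b, so an effect comparable with the planned 0.026 could produce or conceal a finding of about that size.

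This rests on assumed waits, reopening dates and shapes, and on b, none of which the documents give. It does not show that the result will be biased, that surgery has no effect, or that the sample size of 330 is wrong.

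**What to change.** 1. **Section 3.6.1:** pre-specify a sensitivity analysis of the 6-month contrast that adds calendar-month effects without the linear component, by region where the data allow. Staggered surgery dates make these effects estimable.
2. **Optional second version:** a site-specific indicator of restriction period, with a note that it removes the bias only if policy changed in steps.
3. **Interpretation:** state that if the contrasts with and without calendar effects differ materially, the change will not be attributed to surgery alone. State also the assumption that waiting and operated patients share the same calendar effects.
4. **Life-space:** do not adjust the main contrast for postoperative life-space, because surgery itself can change it. Naming it in the time-dependent list in 3.6.2 would close the wording gap.

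The cost is analysis-plan wording, restriction dates by site if the indicator is used, and a larger standard error in the sensitivity analysis only: about 12-20% for month effects and 0-17% for an indicator. No new patient data are needed.
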